9.3.2 Supplementary Estimands for the Primary Endpoint

For the primary analysis, five supplementary estimands will be considered in order to assess the impact of intercurrent events.

Table 2 Supplementary Estimands for the Primary Endpoint

Estimand	EDPS	Intercurrent event		
		Use* of Permitted TCS/TCI Rescue Therapy or Type 1 Prohibited Medications ¹	Study Discontinuation Before Week 16 Visit or Type 2 Prohibited Medications ² Use ³	Noncompliance or Unblinding or Other Protocol Deviations Affecting Efficacy Before Week 16
Supplementary Estimand 1	EDPS2	
If <28 days before Week 16 visit: While-on-treatment strategy Data will be considered missing
 
If ≥28 days before Week 16 visit: Treatment policy strategy (as per primary estimand)
	
If type 2 prohibited medication² used: Composite strategy (as per primary estimand)
 
If due to related** reason: Composite strategy (as per primary estimand)
 
If due to non-related** reason: While-on-treatment strategy (as per primary estimand)
	Treatment policy strategy (as per primary estimand)

Estimand	EDPS	Intercurrent event		
		Use* of Permitted TCS/TCI Rescue Therapy or Type 1 Prohibited Medications ¹	Study Discontinuation Before Week 16 Visit or Type 2 Prohibited Medications ² Use ³	Noncompliance or Unblinding or Other Protocol Deviations Affecting Efficacy Before Week 16
Supplementary Estimand 2	EDPS3	
If <14 days before Week 16 visit: Composite strategy Participant will be considered a non-responder
 
If ≥14 days before Week 16 visit: Treatment policy strategy Data will be used as collected
	
If type 2 prohibited medication² used: Composite strategy (as per primary estimand)
 
If due to related** reason: Composite strategy (as per primary estimand)
 
If due to non-related** reason: While-on-treatment strategy (as per primary estimand)
	Treatment policy strategy (as per primary estimand)
Supplementary Estimand 3	EDPS4	
If <28 days before Week 16 visit: Composite strategy (as per primary estimand)
 
If ≥28 days before Week 16 visit: Treatment policy strategy (as per primary estimand)
	
If type 2 prohibited medication² used: While-on-treatment Strategy Data will be considered missing from the date of medication start
 
If study discontinuation: While-on-treatment strategy Data will be considered missing from the date of treatment discontinuation
	Treatment policy strategy (as per primary estimand)

Estimand	EDPS	Intercurrent event		
		Use* of Permitted TCS/TCI Rescue Therapy or Type 1 Prohibited Medications ¹	Study Discontinuation Before Week 16 Visit or Type 2 Prohibited Medications ² Use ³	Noncompliance or Unblinding or Other Protocol Deviations Affecting Efficacy Before Week 16
Supplementary Estimand 4	EDPS5	As per primary estimand unless data is already excluded due to non-compliance or unblinding or other protocol deviations affecting efficacy	As per primary estimand unless data is already excluded due to non-compliance or unblinding or other protocol deviations affecting efficacy	While-on-treatment strategy Data collected after the intercurrent event will be excluded
Supplementary Estimand 5	EDPS6	Composite strategy Participants with use at any time between Day 1 and the Week 16 visit will be considered as non-responders at all visits after the relevant medication was used.	If type 2 prohibited medication² used: Composite strategy (as per primary estimand) If due to related** reason: Composite strategy (as per primary estimand) If due to non-related** reason: While-on-treatment strategy (as per primary estimand)	Treatment policy strategy (as per primary estimand)

* Consider the last day with therapy for participant before Week 16.

** Treatment discontinuation reasons will be checked. Reasons related to study medication are lack of efficacy, treatment failure, adverse event (if related). Also, withdrawal of consent may be considered related to study medication based on the clarification text provided, that will be assessed by the Evelo team and provided in a separate spreadsheet. Non-related reasons are all other reasons.

¹Prohibited concomitant medications which may affect efficacy requiring the concomitant medication to be immediately discontinued where possible once the use is discovered. Such medications use will be recorded as protocol deviation. Classification will be provided by the sponsor in a separate spreadsheet.

²Prohibited concomitant medications which may affect efficacy requiring IMP discontinuation. Such medications use will be recorded as protocol deviation. Classification will be provided by the sponsor in a separate spreadsheet.

³Type 2 prohibited medication will be considered as treatment withdrawal due to related reason at the date of medication start for the intercurrent event strategy.

9.3.3 Main Analytical Approach

The primary analysis will be performed using a logistic regression model. The model will include parameters for treatment group, baseline vIGA score and baseline EASI score. As described in [Section 9.2](#) additional covariates for baseline factors will be assessed using this model for inclusion in all efficacy models. Only Week 16 data will be included in the model.

Treatment will consist of 4 levels (all placebo, cohort 1 EDP1815, cohort 2 EDP1815, cohort 3 EDP1815). Baseline vIGA will consist of 3 levels (2, 3 and 4).

The following treatment differences will be estimated:

- Cohort 1 EDP1815 vs Pooled placebo
- Cohort 2 EDP1815 vs Pooled placebo
- Cohort 3 EDP1815 vs Pooled placebo
- Cohorts 2+3 EDP1815 vs Pooled placebo*
- All EDP1815 vs Pooled placebo*
- Cohort 2 EDP1815 vs Cohort 3 EDP1815**
- Cohort 1 EDP1815 vs Cohort 2 EDP1815**

* Comparisons between pooled EDP1815 groups and pooled placebo will be considered as secondary analysis.

** Comparisons between EDP1815 treatment groups will be considered as exploratory analysis.

The comparisons between pooled EDP1815 groups* and comparisons between EDP1815 treatment groups** will be done using contrasts (LSMESTIMATE statement) within the relevant SAS procedures.

The actual and predicted probability of EASI-50 response at Week 16 in each treatment group together with the estimated odds ratios and associated confidence intervals for each treatment difference will be displayed. P-values will be displayed for the comparisons of active treatment (individual and pooled) vs pooled placebo.

Vertical bar plots for the actual and predicted probabilities of EASI-50 at Week 16 for each treatment group will be plotted.

The primary analysis approach will be repeated using the 4 supplementary estimands described in [Section 9.3.2](#).

9.3.4 Sensitivity Analyses

Secondary estimand generalised linear mixed effects model (GLMM) analysis of EASI-50 (including all timepoints as described in [Section 9.4.2.2](#)) will be considered a sensitivity analysis for the primary endpoint.

9.3.5 Subgroup Analyses

The analyses described in [Section 9.3.3](#) will be repeated on the primary estimand using the subgroup of baseline vIGA score of 3 as defined in [Section 7.2](#).

For the subgroups of baseline vIGA score other than 3 (baseline vIGA score of 2; baseline vIGA score of 4), number of patients with EASI-50 response will be summarized, but no analysis will be done, as the sample sizes are not expected to be large enough for meaningful comparisons to be made.

There will be no figures for the subgroup analyses.

9.4 Secondary Efficacy Analyses

All efficacy analysis details in this section are provided for cohorts 1-3 analysis.

For cohort 4 analysis the same approach will be used. Any differences and additional analyses will be described in the SAP Addendum.

All continuous and response secondary estimands will use EDPS1 (the primary estimand approach).

Secondary continuous and response endpoints based on the EASI, vIGA and PP-NRS will be analysed with a supportive estimands using EDPS2 (the supplementary estimand 1 approach) and EDPS6 for the response endpoints only (the supplementary estimand 5 approach).

Count secondary endpoints will use EDPS7 (estimand includes all data as collected prior to completion or withdrawal from the study).

The following treatment differences will be estimated:

- Cohort 1 EDP1815 vs Pooled placebo
- Cohort 2 EDP1815 vs Pooled placebo
- Cohort 3 EDP1815 vs Pooled placebo
- Cohorts 2+3 EDP1815 treatment group vs all placebo
- All EDP1815 treatment group vs all placebo
- Cohort 2 EDP1815 vs Cohort 3 EDP1815*
- Cohort 1 EDP1815 vs Cohort 2 EDP1815*

* Comparisons between EDP1815 treatment groups will be considered as exploratory analysis.

The comparisons between pooled EDP1815 groups and comparisons between EDP1815 treatment groups* will be done using contrasts (LSMESTIMATE statement) within the relevant SAS procedures.

Summary statistics only will be presented for Week 20 for those participants who completed treatment but did not wish to participate in the OLE.

9.4.1 Continuous Secondary Endpoints

The following secondary endpoints will be analysed in the same manner as described below:

- Mean absolute change from baseline in EASI score at Weeks 4, 8, 12, and 16
- Mean percentage change from baseline in EASI score at Weeks 4, 8, 12, and 16
- Mean absolute change from baseline in vIGA*BSA score at Weeks 4, 8, 12, and 16
- Mean percentage change from baseline in vIGA*BSA score at Weeks 4, 8, 12, and 16
- Mean absolute change from baseline in BSA score at Weeks 4, 8, 12, and 16
- Mean percentage change from baseline in BSA score at Weeks 4, 8, 12, and 16
- Mean absolute change from baseline in SCORAD score at Weeks 4, 8, 12, and 16
- Mean percentage change from baseline in SCORAD score at Weeks 4, 8, 12, and 16
- Mean absolute change from baseline in DLQI score at Weeks 4, 8, 12, and 16
- Mean percentage change from baseline in DLQI score at Weeks 4, 8, 12, and 16
- Mean absolute change from baseline in POEM score at Weeks 4, 8, 12, and 16
- Mean percentage change from baseline in POEM score at Weeks 4, 8, 12, and 16
- Mean absolute change from baseline in PP-NRS score at Weeks 4, 8, 12, and 16
- Mean absolute change from baseline in SD-NRS score at Weeks 4, 8, 12, and 16

If a participant has a zero score for any of the secondary scores at baseline, that participant will be excluded from any of the percentage change from baseline summaries and analyses as the percentage change from baseline cannot be calculated.

9.4.1.1 Estimands

The population summary measure of interest will be the mean difference between treatment groups specified in [Section 9.4](#).

Where intercurrent event strategy is composite, for continuous endpoints value will be imputed with the last off-rescue observation.

Last off-rescue observation is defined as the last off-rescue observation in the period before the corresponding intercurrent event plus early termination visit in case of early study discontinuation (off-rescue is defined as data collected at least 28 days after use of rescue medication or type 1 prohibited medication).

Note, for PP-NRS and SD-NRS intercurrent event strategy should be applied for daily scores before the weekly scores are calculated.

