7.10. Unscheduled Visits

Unscheduled visits are visits that fall outside of the scheduled visits indicated in the SOA. These visits and the findings are to be recorded on the appropriate eCRFs.

If an unscheduled visit occurs due to the participant requiring rescue therapy, every attempt should be made to conduct efficacy and safety assessments (e.g., EASI, BSA, vIGA, AEs, and concomitant medications) immediately before prescribing/administering any rescue therapy [[Section 6.9.1.2 Rescue Therapy](#)].

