11.1.2. Defined Data Point Sets

The following efficacy data point sets (EDPS) and safety data point sets (SDPS) are defined:

EDPS1: Consists of all data collected at a scheduled timepoint that is at least 28 days after use of topical corticosteroid rescue therapy. Data collected less than 28 days after such use or data missing due to withdrawal from the study for reasons considered related to study medication will be replaced as follows:

- Continuous endpoints: value will be imputed with the last off-rescue observation carried forward (off-rescue is defined as data collected at least 28 days after use of rescue medication)
- Responder endpoints: value will be imputed as non-response.
- Count endpoints: N/A (No count endpoint will use this DPS).

Data missing for other reasons, including early withdrawal from the study due to reasons not considered related to study medication will not be replaced and will be considered as missing.

EDPS2: Consists of all data collected at a scheduled timepoint that is at least 28 days after use of topical corticosteroid rescue therapy. Data collected less than 28 days after such use will be considered as missing and excluded from the analysis. Data missing due to withdrawal from the study for reasons considered related to study medication will be imputed as per DPS1. Data missing for other reasons will not be replaced.

EDPS3: Consists of EASI-50 responses collected at Week 16 that were evaluated at least 14 days after use of topical corticosteroid rescue therapy. Data collected less than 14 days after such use or missing due to withdrawal from the study for reasons considered related to study medication will be imputed as non-response.

EASI-50 response missing for other reasons, including early withdrawal from the study due to reasons not considered related to study medication will not be replaced and will be considered as missing.

EDPS4: Consists of EASI-50 responses collected at Week 16 that were evaluated at least 28 days after use of topical corticosteroid rescue therapy. Data collected less than 28 days after such use will be replaced as per DPS1. Data missing due to other reasons including early withdrawal from the study for any reason will not be replaced and be considered as missing.

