11.3.2. Secondary Estimands

All continuous and response secondary estimands will use EDPS1 which uses a composite strategy for the use of topical corticosteroid rescue therapy less than 28 days before the relevant visit and for data missing due to withdrawal from the study due to a reason considered as related to study medication. For intercurrent events relating to compliance with the study medication, emollient use, unblinding or use of prohibited medications, a treatment policy strategy and data will be analyzed as collected.

Secondary endpoints based on the EASI, vIGA and PP-NRS endpoints will be analyzed with a supportive estimand using EDPS2, which uses a while-on-treatment strategy for rescue medication and excludes any data collected less than 28 days after rescue medication use. In addition, for responder endpoints relating to EASI, vIGA and PP-NRS a further supportive estimand using EDPS6 will be analyzed where all timepoints after any use of rescue medication will be considered as a non-responder.

Secondary count endpoints will use EDPS7 which includes all data as collected prior to completion or withdrawal from the study. As rescue medication use forms part of these endpoints it is not considered as an intercurrent event.

The following treatment differences will be estimated for each estimand in Cohorts 1-3:

- EDP1815 1.6x10¹¹ QD (Cohort 1) vs Cohorts 1-3 Pooled placebo
- EDP1815 6.4x10¹¹ QD (Cohort 2) vs Cohorts 1-3 Pooled placebo
- EDP1815 3.2x10¹¹ BID (Cohort 3) vs Cohorts 1-3 Pooled placebo
- EDP1815 6.4x10¹¹ Daily (Cohorts 2 and 3) vs Cohorts 1-3 Pooled placebo
- All EDP1815 (Cohorts 1, 2 and 3) vs Pooled placebo
- EDP1815 6.4x10¹¹ QD (Cohort 2) vs EDP1815 3.2x10¹¹ BID (Cohort 3)*
- EDP1815 1.6x10¹¹ QD (Cohort 1) vs EDP1815 6.4x10¹¹ QD (Cohort 2)*

* The final two comparisons between active treatment groups will be considered as exploratory and only estimates and confidence intervals of such comparisons will be shown.

The following treatment differences will be estimated for each estimand in Cohort 4:

- EDP1815 8.0x10¹⁰ QD (Cohort 4) vs Cohort 4 Matched Placebo
- EDP1815 8.0x10¹⁰ QD (Cohort 4) vs EDP1815 1.6x10¹¹ QD (Cohort 1)**

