As collected	As collected	Imputed with Week 2 data because there was a rescue therapy within 28 days before Week 4 visit and the last off-rescue data is at Week 2 visit	As collected	Imputed with Week 9 data because there was a rescue therapy within 28 days before Week 12 visit and the last off-rescue data is at unscheduled Week 9 visit	Imputed with Week 9 data because visit is missing due to reasons considered related to study medication and the last off-rescue data is at unscheduled Week 9 visit

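### For continuous secondary scores the declared composite strategy is really a carry-forward of the last off-rescue value, which can credit a rescued participant with a score from before the flare; SCORAD, DLQI and POEM are the most exposed and have no supportive analysis

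*SAP*

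**What the plan says.** Protocol 11.3.2 states: "All continuous and response secondary estimands will use EDPS1 which uses a composite strategy". The trigger there is topical corticosteroid rescue less than 28 days before the visit, or data missing after a treatment-related withdrawal. The SAP adds topical calcineurin inhibitors and type 1 prohibited medication.

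For responder endpoints, EDPS1 imputes non-response. For continuous endpoints, Protocol 11.1.2 gives a different rule: "Continuous endpoints: value will be imputed with the last off-rescue observation carried forward". SAP 9.4.1.1 repeats it: "Where intercurrent event strategy is composite, for continuous endpoints value will be imputed with the last off-rescue observation". The SAP defines the carried value as follows: "Last off-rescue observation is defined as the last off-rescue observation in the period before the corresponding intercurrent event plus early termination visit", where "off-rescue is defined as data collected at least 28 days after use of rescue medication or type 1 prohibited medication".

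What is measured at the moment of rescue differs by instrument:

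- **EASI, vIGA, BSA.** Protocol 7.10 says that before rescue at an unscheduled visit "every attempt should be made to conduct efficacy and safety assessments (e.g., EASI, BSA, vIGA, AEs, and concomitant medications" should be obtained. SAP 7.7 lets these data feed the carry-forward.
- **PP-NRS, SD-NRS.** These come from a daily diary, and SAP 9.4.1.1 applies the rule to the daily scores.
- **SCORAD, DLQI, POEM.** Table 4-1 schedules these at every visit from Day 1 and at early termination, but not at the rescue visit.

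SAP 9.4.1.2 runs the supportive EDPS2 model, which sets post-rescue values to missing, only for endpoints based on EASI, vIGA and PP-NRS.

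**The concern.** A composite strategy builds the event into the outcome. Here rescue is given for unacceptable worsening of atopic dermatitis (Protocol 6.9.1.2), so a composite value should be unfavourable. The responder rule achieves that. The continuous rule does not: rescue itself costs the participant nothing, and the score used may predate the worsening.

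Two things follow. First, one participant at one visit can be a SCORAD-50 non-responder and also contribute a large percentage improvement in SCORAD; DLQI and POEM have the same split. Second, the size of the continuous EASI change can depend on whether a best-efforts extra visit took place. If rescue is commoner on placebo, the rule flatters placebo and shrinks the estimated benefit. The SAP describes the study's focus as estimation of treatment effects, so bias in either direction matters.

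**Working it through.** **1. Reproduce the SAP's own example (7.1.2.1, Example 3, continuous endpoint).** Visit days from Table 4-1: Week 2 = 15, Week 4 = 29, Week 8 = 57, Week 12 = 85, Week 16 = 113. Assumed dates within the example's weeks: rescue on Days 16–21 and 64–70, unscheduled visit on Day 63 before the second course only, withdrawal for lack of efficacy after Week 12. An observation is off-rescue if it is at least 28 days after the last rescue day.

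| Visit | Days since last rescue | EASI source | SCORAD/DLQI/POEM source |
|---|---|---|---|
| Week 4 | 29 − 21 = 8 | Week 2 | Week 2 |
| Week 8 | 57 − 21 = 36 | as collected | as collected |
| Week 12 | 85 − 70 = 15 | unscheduled Week 9 | Week 8 |
| Week 16 | missing, related withdrawal | unscheduled Week 9 | Week 8 |

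The EASI column matches the SAP, which says "Imputed with Week 2 data" for Week 4 (no rescue visit done) and uses the unscheduled Week 9 data for Weeks 12 and 16. The last column applies the same rule to scores that the rescue visit does not collect: the carried value is from Week 8, before the rescue assessment.

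**2. Other timings.**

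- *Rescue between visits, Days 100–106.* Week 16 is 113 − 106 = 7 days later, so it is replaced. EASI comes from the Day 100 rescue visit; SCORAD, DLQI and POEM come from Week 12, which is 15 days earlier.
- *Rescue started at the Week 12 visit, Days 85–91.* Week 16 is 113 − 91 = 22 days later. All scores come from Week 12, the flare assessment, if a same-day assessment counts as pre-rescue. The SAP does not state that ordering.
- *Treatment failure without recent rescue.* The early termination visit supplies the value for all three scores.
- *Closely spaced courses, Days 16–22, 40–46, 68–74 and 95–101.* The later rescue visits fall 40 − 22 = 18, 68 − 46 = 22 and 95 − 74 = 21 days after the previous course. None is off-rescue. Scheduled visits from Week 4 on fall 7, 11, 11 and 12 days after a course. Week 16 EASI therefore comes from a Day 16 visit before the first course (113 − 16 = 97 days earlier), or from Week 2 if that visit was missed.

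**3. One participant (illustrative values).** Baseline EASI 16, Week 8 EASI 6, flare EASI 18, rescue in week 10. Week 12 percentage change:

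- rescue visit missed: (6 − 16)/16 = −62.5%
- rescue visit done: (18 − 16)/16 = +12.5%

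The gap is 75 points at Week 12. If the participant stays in the study, Week 16 is used as collected, because 113 − 70 = 43 days.

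**4. Arm level.** The documents give no rescue rates, so both inputs are assumptions. Shift in an arm's mean = share of the arm whose carried value predates the flare × gap (flare minus carried percentage change).

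| Share affected | Gap 20 | Gap 40 | Gap 60 |
|---|---|---|---|
| 5% | 1.0 | 2.0 | 3.0 |
| 10% | 2.0 | 4.0 | 6.0 |
| 20% | 4.0 | 8.0 | 12.0 |
| 30% | 6.0 | 12.0 | 18.0 |

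Between-arm bias is the difference of the two arms' shifts. With 25% affected on placebo, 15% on active and a gap of 45 in both, it is 0.25 × 45 − 0.15 × 45 = 11.25 − 6.75 = 4.5 points. With equal shares and gaps it is zero.

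**The case against.** The rule is openly specified in both documents with a worked example, it touches only continuous secondary endpoints, and several safeguards exist. For EASI, vIGA and BSA the rescue visit normally supplies the flare value. PP-NRS and SD-NRS use daily scores. The SCORAD, DLQI and POEM responder endpoints already impute non-response under EDPS1, and rescue use is analysed directly as a proportion, as courses and as days. EASI, vIGA and PP-NRS also have EDPS2. If placebo needs more rescue, the bias runs against the sponsor's drug. All of this stands, and it limits the point to some scores and some timings.

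Three stronger readings are tempting but not supported:

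- *SCORAD, DLQI and POEM always carry a pre-flare value.* They do not when rescue starts at a scheduled visit or when an off-rescue early termination visit supplies the value.
- *A missed rescue visit turns an EASI failure into a success.* EASI-50 is non-response either way; only the size of the continuous change varies.
- *EDPS1 must be replaced by the worse of baseline and the last off-rescue value.* In the example above this gives 0% without the rescue visit and +12.5% with it, so some visit dependence remains. It can also overwrite a score measured just before rescue with a worse baseline.

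What the objection does not answer is the label, the conflict with the responder rule, and the absence of any alternative analysis of the continuous scores that the rescue visit never collects.

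**Conclusion.** The point holds in a limited form. For continuous secondary endpoints the rule is not composite: it does not make rescue unfavourable, and it disagrees with the responder rule for the same instruments.

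A value from before the current flare is carried for SCORAD, DLQI and POEM when rescue starts between scheduled visits. For EASI, vIGA and BSA it is carried when the pre-rescue visit is missed or lies within 28 days of an earlier course; in the latter case the carried value may itself come from an earlier flare. Only visits under 28 days after rescue or type 1 use are replaced, together with visits missing after a related withdrawal that has no off-rescue early termination value. There is credit only if the carried value improved on baseline.

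The size is an assumption: 1 to 18 percentage points per arm over the range shown. The sign and size of any between-arm bias cannot be fixed from the documents. A reader might infer an established loss of 4.5 points, but that figure is one assumed scenario. The primary analysis is unaffected.

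**What to change.** - In SAP 9.4.1.2, extend the existing EDPS2 MMRM to absolute and percentage change in SCORAD, DLQI, POEM and BSA.
- In Protocol 11.3.2 and SAP 7.1.2.1 and 9.4.1.1, stop describing the carry-forward as composite for continuous endpoints. Describe it as use of the last off-rescue value, and state how a same-day assessment and rescue start are ordered.
- Optionally, add a supportive analysis using the worse of baseline and the last off-rescue value as a true composite. It need not replace EDPS1.

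The cost is a few extra model runs and a text change, with no new data. EDPS2 has limits. It treats values after rescue as missing at random, which is doubtful when rescue follows worsening. It does not make rescue unfavourable either. It also still imputes as in EDPS1 after related withdrawal or type 2 medication. It is a check on the rescue carry-forward, not a composite analysis.

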5.3.3.8 Peak Pruritus Numerical Rating Scale (PP-NRS)

The Peak Pruritus Numerical Rating Scale (PP-NRS) is a scale from 0 to 10 for participants to rate their worst itch that they have experienced over the previous 24 hours. The PP-NRS will be completed as a part of daily symptom diary from the Screening Visit to end of study.

PP-NRS score at each visit is calculated as the mean itch daily score for the 7 days prior to and including the visit date. At least 4 daily scores must be available for the score at the relevant visit to be considered evaluable.

PP-NRS responses are defined as a reduction of ≥ 2 and ≥ 4 in the PP-NRS score if a participant has a score of ≥ 2 and ≥ 4 , respectively, at baseline (a ≥ 2 -4-point change from baseline is considered the minimal clinically important difference threshold).

Sustained PP-NRS response is defined as one which is present at all available assessments within at least 14 days period. Sustained response is considered to have been first achieved at the first of the consecutive days.

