7.1.2.1 Efficacy Data Point Set 1 (EDPS1)

EDPS1 consists of all data collected at a scheduled timepoint that is at least 28 days after use of TCS/TCI rescue therapy* or type 1 prohibited medication and before use of type 2 prohibited medication. Data collected less than 28 days after such use or data missing due to withdrawal from the study for reasons considered related to study medication** or data collected after use of type 2 prohibited medications will be replaced as follows:

- Continuous endpoints: value will be imputed with the last off-rescue¹ observation in the period before the event plus early termination visit in case of early study discontinuation (off-rescue is defined as data collected at least 28 days after use of rescue medication or type 1 prohibited medication)
- Responder endpoints: value will be imputed as non-response.
- Count endpoints: N/A (no count endpoint will use this DPS).

Data missing for other reasons, including early withdrawal from the study due to reasons not considered related to study medication will not be replaced and will be considered as missing.

Example 1: if patient completed 16 weeks of study with rescue therapy during week 3 and then during week 10 then responder endpoints will be analysed as shown in table:

Week 0	Week 2	Week 4	Week 8	Week 12	Week 16
As collected	As collected	Imputed as non-responder because there was a rescue therapy within 28 days before Week 4 visit	As collected	Imputed as non-responder because there was a rescue therapy within 28 days before Week 12 visit	As collected

Example 2: if patient completed 16 weeks of study with rescue therapy from Day 25 to Day 31 then responder endpoints will be analysed as shown in table:

Week 0	Week 2	Week 4	Week 8	Week 12	Week 16
As collected	As collected	Imputed as non-responder because there was a rescue therapy within 28 days before Week 4 visit	Imputed as non-responder because there was a rescue therapy within 28 days before Week 4 visit	As collected	As collected

Example 3: if patient withdrew study early due to the lack of efficacy after 12 weeks of treatment with rescue therapy during week 3 (unscheduled rescue therapy visit was not done) and then during week 10 (unscheduled rescue therapy visit was done at Week 9 prior to the rescue therapy start) then continuous endpoints will be analysed as shown in table:

Week 0	Week 2	Week 4	Week 8	Week 12	Week 16

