7.1.2.2 Efficacy Data Point Set 2 (EDPS2)

EDPS2 consists of all data collected at a scheduled timepoint that is at least 28 days after use of TCS/TCI rescue therapy* or type 1 prohibited medication and before use of type 2 prohibited medication. Data collected less than 28 days after such use will be considered as missing and excluded from the analysis. Data missing due to withdrawal from the study for reasons considered related to study medication** and data after use of type 2 prohibited medication will be imputed as per EDPS1. Data missing for other reasons will not be replaced.

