9.4.2.1 Estimands

The population summary measure of interest will be the odds ratio between treatment groups specified in [Section 9.4](#) for the achievement of response at the relevant time point.

Note, for PP-NRS and SD-NRS intercurrent event strategy will be applied after weekly scores at scheduled visits are calculated from daily scores.

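### PP-NRS and SD-NRS change scores apply rescue handling before weekly averaging, while response scores apply it after, so some change scores rest on one pre-rescue day and some visits are treated differently in the two analyses

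*SAP*

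**What the plan says.** SAP 5.3.3.8 defines one visit score for itch: "PP-NRS score at each visit is calculated as the mean itch daily score for the 7 days prior to and including the visit date". It adds a completeness rule: "At least 4 daily scores must be available for the score at the relevant visit to be considered evaluable". SAP 5.3.3.9 repeats both for SD-NRS. Baseline for daily endpoints is also a 7-day average with at least 4 values (SAP 5.3.1.2).

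The order of operations then differs by endpoint type.

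- **Change from baseline (SAP 9.4.1.1):** "for PP-NRS and SD-NRS intercurrent event strategy should be applied for daily scores before the weekly scores are calculated". Imputation follows the general rule: "Where intercurrent event strategy is composite, for continuous endpoints value will be imputed with the last off-rescue observation", where "off-rescue is defined as data collected at least 28 days after use of rescue medication or type 1 prohibited medication".
- **Response (SAP 9.4.2.1):** "for PP-NRS and SD-NRS intercurrent event strategy will be applied after weekly scores at scheduled visits are calculated from daily scores". Under EDPS1 (SAP 7.1.2.1), "Responder endpoints: value will be imputed as non-response".

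The supportive EDPS2 analysis (SAP 7.1.2.2) covers PP-NRS but not SD-NRS. It does not impute after rescue: "Data collected less than 28 days after such use will be considered as missing and excluded from the analysis".

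Protocol Table 11-2 defines the 7-day mean but gives no order. The table of changes in SAP Section 13 does not mention one.

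**The concern.** The visit score is meant to be a 7-day mean. If daily scores are replaced before averaging, a week that lies wholly within 28 days after rescue is filled with copies of the last off-rescue daily score. The mean of identical copies is that one score. The change endpoint then subtracts a multi-day baseline average from a single day.

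Two consequences follow.

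- A single day is more variable than a 7-day mean. Protocol 6.9.1.2 allows rescue for worsening that has become unacceptable, so the last day before rescue is probably higher than that participant's usual level. The error would count against whichever arm uses more rescue.
- At some visits the change table and the response table use different data for the same participant.

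**Working it through.** **Inputs.** 7-day window ending on the visit day, minimum 4 scores (SAP 5.3.3.8, 5.3.3.9); 28-day rescue window (SAP 9.4.1.1, 7.1.2.1); rescue courses of up to 7 days (Protocol 6.9.1.2). A day counts as on-rescue if it lies in the course or less than 28 days after its last day. Treating the first rescue day as pre-rescue shifts the counts below by about one position.

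**Step 1: reproduce SAP Example 2 (7.1.2.1), rescue Days 25 to 31.** Applied to the visit day, the rule marks Weeks 4 and 8 as non-response and leaves Weeks 2, 12 and 16 as collected. This agrees with the SAP.

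**Step 2: apply the change rule to the same example, with complete diaries.**

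- Week 8 (Days 51–57) lies 20 to 26 days after Day 31. All 7 scores are replaced by the Day 24 score, so the weekly mean equals Day 24.
- Week 4 (Days 23–29): Days 25–29 are replaced by Day 24. The score is (Day 23 + 6 × Day 24)/7.

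**Step 3: every timing of one 7-day course that touches a visit window (40 timings).**

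| Situation | Timings | Change score | Response score |
|---|---|---|---|
| Rescue began on or before first window day; visit <28 days after last rescue day | 28 (70%) | one daily score | non-response |
| Rescue began inside the window | 6 (15%) | mixture | non-response |
| Visit 28–33 days after last rescue day | 6 (15%) | mixture | as collected |

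In the last row, with a gap of g days, the number of replaced days is 34 − g: 6, 5, 4, 3, 2 and 1 for g = 28 to 33. The response analysis replaces none. Under EDPS2 at g = 28, 29 or 30, only 1, 2 or 3 daily scores remain. That is below the minimum of 4, so the PP-NRS change score is not evaluable while the response is analysed.

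**Step 4: illustrations with assumed scores (baseline 7, last pre-rescue day 9).**

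- Visit at g = 28, post-rescue level 3 to 5. Change: (6 × 9 + 3)/7 − 7 = +1.1, to (6 × 9 + 5)/7 − 7 = +1.4. Response uses 3 − 7 = −4 to 5 − 7 = −2, which meets the 2-point threshold.
- Fully replaced week. As written: 9 − 7 = +2.0. Carrying a 7-day mean whose other six days are at 5 to 7: (6 × 5 + 9)/7 − 7 = −1.4, to (6 × 7 + 9)/7 − 7 = +0.3.

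**Step 5: precision.** With equal correlation ρ between days, the variance of one day relative to a 7-day mean is 1/(ρ + (1 − ρ)/7): 1.75, 1.35 and 1.09 for ρ = 0.5, 0.7 and 0.9.

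**Step 6: size of the upward selection.** The documents give none of these inputs. Assume daily scores with mean 6 and SD 1.5, capped to 0–10, rescue after a day scored 8 or more, and first-order autoregressive correlation between days. Simulated excess of the trigger day over the 7-day mean ending that day:

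| Correlation | Excess (points) | × 0.10 difference in rescue use | × 0.70 fully replaced |
|---|---|---|---|
| 0 | 2.3 | 0.23 | 0.16 |
| 0.7 | 1.5 | 0.15 | 0.105 |
| 0.9 | 0.7 | 0.07 | 0.05 |

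The third column treats every extra rescued participant as fully replaced at that visit. The fourth takes 70% from Step 3, as if all timings were equally likely, and counts mixtures as zero.

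**The case against.** The case for leaving the rule alone has several parts.

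- **Carrying a pre-rescue value forward is the SAP's general rule.** Protocol 6.9.1.2 asks for assessments just before rescue, Example 3 in SAP 7.1.2.1 carries such a visit forward, and SAP 7.7 admits these visits for that purpose. This stands. What is specific to itch and sleep is that one day replaces a 7-day mean.
- **Each order has a plausible rationale.** Non-response can only be set at visit level, so 9.4.2.1 is natural. Daily imputation keeps the weekly means consistent with the daily EDPS1 endpoints (SAP 9.5.1.1) and applies the 28-day window exactly. This explains the choice but does not justify comparing one day with a baseline mean.
- **EDPS2 would expose an effect of the carried score on PP-NRS change.** It would in part, but there is no such analysis for SD-NRS, and EDPS2 has its own mismatch at 28 to 30 days.
- **The reach is small.** These are two of the 14 continuous secondary endpoints in SAP 9.4.1, in a study focused on estimation with no multiplicity control (SAP 7.6).

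A reader might also infer that an imputed week always satisfies the 4-of-7 rule. The documents do not support that. EDPS1 replaces scores that were collected within 28 days of rescue and leaves values missing for other reasons as missing. A skipped diary day therefore stays missing and the minimum still applies; only days missing through treatment-related withdrawal are filled.

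**Conclusion.** The two sections state opposite orders for the same score, and the consequences follow from the SAP's own rules. A single pre-rescue day stands in for the week in the first situation of Step 3; elsewhere the score is a mixture.

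A reader might go further and conclude that every rescued participant's mean becomes one score, or that the two analyses disagree whenever rescue is used. Neither holds. In fully replaced weeks both analyses treat the visit as rescue-affected, and the contrast between a carried score and non-response comes from EDPS1. Disagreement caused by the order is limited to visits 28 to 33 days after rescue and to rescue that starts inside the window.

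The upward direction is an inference from why rescue is given. The size, about 0.7 to 2.3 points per fully imputed participant and about 0.05 to 0.2 points in the mean difference, rests on the assumed daily SD, trigger, correlation and 10-point difference in rescue use. It shrinks as day-to-day correlation rises.

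The primary EASI-50 analysis and the sample size are unaffected. The rule should be corrected, but it does not threaten the main conclusion.

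**What to change.** In SAP 9.4.1.1, calculate the weekly score first and classify the visit by the same less-than-28-days rule that 9.4.2.1 uses. Where EDPS1 calls for imputation, use the last off-rescue 7-day mean: the 7 days ending the day before rescue, with at least 4 scores. If that is not available, use the last evaluable off-rescue visit score. The exploratory daily endpoints can stay at daily level.

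Of the 40 timings in Step 3, the two analyses differ in how they treat the visit in 12 (6 + 6) as written and in none after the change.

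The cost is SAP wording and programming; the daily diary data are already collected. The downside is that at visits 28 to 33 days after rescue, 6 to 1 diary days inside the 28-day window enter the mean, as they already do for the response endpoints.
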